STUDY PROTOCOL AND STATISTICAL ANALYSIS PLAN

Using a randomized control trial to evaluate the effectiveness of glove changing in reducing wound-related complications following cesarean section in Vietnam

Principle investigator	[name] Obstetrician – Gynecologist Hung Vuong hospital Ho Chi Minh city, Vietnam
Protocol identification number	CK62721303 (dated September 14, 2020)

Abbreviations

CS	Cesarean section
SSI	Surgical site infection
CPR	Cardiopulmonary resuscitation
ASA	American Society of Anesthesiologists
NYHA	New York Heart Association

Table of contents

1. Introduction 4

2. Study design 4

3. Aims and objectives 6

4. Outcomes 6

5. Populations and subgroups to be analyzed 6

6. Analyses 6

7. References 6

1. Introduction

[figure not shown]
The aim of this study is to investigate the effect of glove changing on wound complications after cesarean surgery in Vietnam. We hypothesize that changing gloves prior to abdominal closure reduces the incidence of infectious complications following cesarean surgery.

2. Study design

Study subjects will be recruited from December 2020 to February 2021 at Hung Vuong hospital, Ho Chi Minh city, Vietnam. Inclusion criteria for participants in this study include pregnant women who are 18 years old or higher; who have CS performed at Hung Vuong hospital; and who live close to Ho Chi Minh city and agree to return for postpartum care one-month post-surgery. Exclusion criteria include pregnant women who have fever during labor; who have systemic infectious conditions; who have surgical site infection SSI or sexually infectious conditions; who have ongoing internal conditions such as pre-eclampsia, severe anemia, American Society of Anesthesiologists (ASA) ≥ 3 , New York Heart Association (NYHA) class 3 or above, pulmonary edema, or severe asthma. Data collection will be stopped when pregnant women require cardiopulmonary resuscitation (CPR) or have damaged pelvic organs during CS; when they need extra surgery after CS; or when the surgical team has double gloving or the gloves get punctured during surgery.

The study is a parallel-group randomized control trial with 2 arms. Arm 1 includes patients who will have glove changed prior to abdominal closure during CS. Arm 2 includes patients who will not have glove changed prior to abdominal closure during CS. All patients are randomized using computer-generated sequences with allocation ratio 1:1. Clinic visits are performed at 2 time points, unless emergency check-up is recommended after hospital discharge. Visit 1 is at 2-3 days post-surgery and visit 2 is at 30 ± 2 days post-surgery where primary and secondary outcomes are measured. The study is concluded when we finish the second data collection or when patients are discharged from the hospital after a required immediate check-up. Patients who do not return for postpartum care will be considered lost to follow up. The study design is visualized in Figure 1 below.

Figure 1: The CONSORT flow diagram of the study

Sample size calculation

The sample size is calculated based on the following formula:

$$n = \frac{\left(Z_{1-\frac{\alpha}{2}}\sqrt{2P(1-P)} + Z_{1-\beta}\sqrt{P_1(1-P_1) + P_2(1-P_2)} \right)^2}{(P_1 - P_2)^2}$$

Where:

n: required minimum sample size in each group

P1: rate of superficial SSI in group 1 (i.e., glove change group)

P2: rate of superficial SSI in group 2 (i.e., control, or usual care group)

$$P = \frac{P_1 + P_2}{2}$$

α : type I error, $\alpha = 0,05 \rightarrow Z_{1-\alpha/2} = 1,96$

β : type II error, $\beta = 0,15$ (statistical power = 0,85) $\rightarrow Z_{1-\beta} = 1,04$

Based on the results from Scrafford's group where they reported the rates of superficial SSI in the glove change group and the usual care group were 6.4% and 13.6%, respectively [1], we will calculate the sample size for each group. In order to achieve the statistical power of 0.85, the required minimum sample size in each group is 310. To account for 5% of the sample lost

during the study, the sample size in each group is increased to 327 based on the calculation $310/0.95=327$. Thus, the required minimum sample size for both groups in our study will be $327*2=654$.

3. Aims and objectives

The aims are 1) to evaluate whether changing gloves during CS reduces complications and SSI, and 2) to identify other factors that are associated with complications and SSI.

4. Outcomes

The primary outcomes of interest are any wound complications occurring after the surgery, including seroma, hematoma, wound separation, and wound infection. Secondary outcomes are any signs of SSI, including fever, swelling, redness, and pain surrounding the incisional area. The outcomes will be evaluated during clinic visits by qualified medical practitioners who are blind to the intervention group assignment.

5. Populations and subgroups to be analyzed

Populations: intention-to-treat

Subgroups: the glove change and usual care group. These 2 subgroups will be analyzed using intention-to-treat populations.

6. Analyses

Data will be analyzed using Stata 16 (StataCorp LLC, College Station, TX). Normally distributed data will be expressed as mean \pm standard deviation, while non-normally distributed data will be shown as medians with interquartile ranges. T-test for normally distributed continuous variables and Mann-Whitney-U test for non-normally distributed continuous variables will be used to compare between groups. Categorical variables will be reported as absolute numbers and percentages; the Chi-square test or Fisher's exact test will be utilized for comparison. A p -value of <0.05 will be considered statistically significant. Multiple logistics regression analysis will be performed to identify factors affecting the superficial incisional complications.

7. References

[1] J. D. Scrafford, B. Reddy, C. Rivard, and R. I. Vogel, "Effect of intra-operative glove changing during cesarean section on post-operative complications: a randomized controlled trial," *Arch Gynecol Obstet*, vol. 297, no. 6, pp. 1449–1454, Jun. 2018, doi: 10.1007/s00404-018-4748-y.

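### Data collection stops at any further surgery after cesarean, even when a primary-outcome wound complication is the cause, and no rule says that the complication is counted

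*Combined protocol and SAP*

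**What the plan says.** Section 2 lists events at which data collection stops. One is "when they need extra surgery after CS". It has no stated cause, no time window and no exception. The other triggers in that sentence concern events during the operation and are not at issue here.

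Section 4 defines the endpoint: "The primary outcomes of interest are any wound complications occurring after the surgery, including seroma, hematoma, wound separation, and wound infection". It also says how the endpoint is ascertained: "The outcomes will be evaluated during clinic visits by qualified medical practitioners".

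On timing, section 2 gives a first visit at 2-3 days and says that "visit 2 is at 30 ± 2 days post-surgery where primary and secondary outcomes are measured". It adds: "Clinic visits are performed at 2 time points, unless emergency check-up is recommended after hospital discharge". The study may also end "when patients are discharged from the hospital after a required immediate check-up".

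Section 5 names the intention-to-treat population and says of the two arms: "These 2 subgroups will be analyzed using intention-to-treat populations". It does not define the population further or give a rule for missing outcomes. The only missing-outcome category in the text is loss to follow-up, in section 2, for women who fail to come back for postpartum care.

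**The concern.** Three of the four named components of the primary outcome (hematoma, wound separation, wound infection) are possible reasons for a further operation. For such a woman, the event the trial is meant to count is also the event that ends her data collection.

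Any loss that follows depends on the outcome, which makes it different from ordinary loss to follow-up. It removes events rather than a cross-section of women, and the 5% sample size allowance does not address that. If the same share of events is lost in each arm, the reported complication rates, the risk difference and the power all fall, while the odds ratio and relative risk barely change. If the share differs between arms, the ratio is biased in a direction that cannot be known in advance.

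The text also leaves classification open. Two teams following it could record the same woman as an event, as a non-event, or as excluded, and could make that choice after seeing the data.

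**Working it through.** **1. Tracing one woman through the text.** Suppose a wound complication leads to further surgery.

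- Recorded at the day 2-3 visit before the surgery: it may still count, because the stop rule does not say that earlier data are discarded.
- Recorded at an emergency check-up: it may count, because the clinic-visit sentence can be read as making that check-up an outcome visit. The text does not say that outcomes are recorded there.
- First found at the re-operation, or not yet recorded at any clinic visit: section 4 ties ascertainment to clinic visits and collection has stopped, so the event can be lost.

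No legible sentence settles any of these cases. Figure 1, the flow diagram, is not reproduced in the text available.

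**2. Reproducing the plan's own figure.** Inputs from section 2: P1 = 0.064, P2 = 0.136, P = 0.10, Z values 1.96 and 1.04.

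- n = (1.96 × √0.18 + 1.04 × √0.177408)² / 0.072² = (0.8316 + 0.4380)² / 0.005184 = 310.9. The plan states 310.
- 310 / 0.95 gives 327 per arm and 654 in total, as stated.
- Power at 310 per arm is 0.850.
- Expected events: 310 × 0.064 = 19.8 (glove change) and 310 × 0.136 = 42.2 (control).
- Risk difference 7.2 points, relative risk 0.471, odds ratio 0.434.

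**3. Illustrating a loss.** Let f be the share of events lost. The documents give no re-operation rate, so f is an assumption, and no value from 2% to 20% is supported by the text. The planning rates are for superficial SSI and stand in for the composite.

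- Reading A, triggering event kept: nothing changes, power 0.850.
- Reading B, woman excluded: rate = p(1−f)/(1−pf), with n(1−pf) women analysed.
- Reading C, woman kept without an event: rate = p(1−f), n = 310.

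Equal f in both arms:

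| f | Events lost, glove / control | B: power | B: risk difference (points) | C: power | C: risk difference (points) |
|---|---|---|---|---|---|
| 2% | 0.4 / 0.8 | 0.843 | 7.08 | 0.842 | 7.06 |
| 5% | 1.0 / 2.1 | 0.833 | 6.91 | 0.829 | 6.84 |
| 10% | 2.0 / 4.2 | 0.814 | 6.61 | 0.806 | 6.48 |
| 20% | 4.0 / 8.4 | 0.771 | 6.00 | 0.754 | 5.76 |

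Under B the odds ratio stays at 0.434 and the relative risk moves only from 0.471 to 0.464 at f = 20%. Under C the relative risk stays at 0.471 and the odds ratio moves only to 0.442.

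For comparison, losing the same number of women at random gives power of 0.849, 0.848, 0.846 and 0.843. The fall in power therefore comes mainly from selection on the outcome, not from the number of women lost.

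**4. Loss in one arm only (reading B, true relative risk 0.471).**

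- f = 2%: 0.479 if control events are lost, 0.462 if glove-arm events are lost.
- f = 5%: 0.492 (0.064 / 0.1301) or 0.448 (0.0610 / 0.136).

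**The case against.** The best defence is that nothing is actually lost. The rule stops collection; it does not exclude the woman or discard her data. The endpoint is binary, so if a wound complication is the reason for surgery, the event has already occurred and needs no later data. The breadth of the outcome definition, the intention-to-treat label and the emergency check-up route all fit with counting it. This stands as a possible reading, and on it no triggering event is lost. It remains an inference: none of those sentences mentions further surgery, and it does not cover a complication first found at re-operation.

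Two other readings are open. The trigger may mean only an immediate further operation, since it sits among intra-operative events, or Figure 1 may show how stopped women are handled. The text sets no time window that would confirm the first, and the second cannot be checked from the text available.

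On size, the objection is largely right. The shares are assumed and the effect at 2% is negligible. Ratio bias needs a difference between arms, and the rule is the same in both arms with blinded assessors, so no specific cause of asymmetry can be named.

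On remedy, it can be argued that a counting rule alone would close most of the gap, and that a second closure not covered by the randomised glove change is a reason to stop observing. It is a fair point that continued follow-up needs a stated rule for complications arising only after re-operation. Continued follow-up is still what the plan's own intention-to-treat population calls for.

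**Conclusion.** The concern holds. As written, the plan can stop measuring a woman because she has had the primary outcome, and no legible passage requires that outcome to be counted. The stop creates missing data; it is not in itself a breach of intention-to-treat, and the text does not show that events will certainly be lost.

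The size is uncertain and may be small. It ranges from nothing, if the triggering event is kept, to power of 0.77 or 0.75 if 20% of events were lost equally in both arms. These figures rest on an assumed share and on superficial SSI rates standing in for the composite. The point should be fixed because the loss would be selected by outcome, only about 20 and 42 events are expected in the two arms, and the remedy is cheap. Confidence is medium, given the more favourable readings and the figure that could not be seen.

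**What to change.** - **Section 2:** remove "when they need extra surgery after CS" from the data-collection stop rules. Keep these women in their randomised arm and collect outcomes to the day-30 visit already scheduled. State whether an emergency check-up is an outcome-recording visit, and align the clinic-visit and study-conclusion sentences with that.
- **Section 4:** state that a wound complication that leads to, or is found at, re-operation counts as a primary outcome event. State also whether a complication arising only after re-operation counts.
- **Section 5:** state how women with further surgery enter the intention-to-treat analysis.

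This concerns data collection and outcome counting only, not clinical management. The cost is about one sentence per section and following a few more women to a visit already in the schedule. It needs no extra patients or procedures.

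### Stopping data collection for double gloving or punctured gloves conflicts with the intention-to-treat analysis and may bias the comparison if removals differ by arm

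*Combined protocol and SAP*

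**What the plan says.** Section 2 (Study design) gives inclusion criteria, then exclusion criteria, then a separate sentence on stopping data collection. That sentence starts with "Data collection will be stopped when pregnant women require cardiopulmonary resuscitation (CPR) or have damaged pelvic organs during CS", goes on to "when they need extra surgery after CS", and ends with "when the surgical team has double gloving or the gloves get punctured during surgery". It describes no further follow-up for these women.

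The same section defines the arms by whether gloves are changed: "Arm 1 includes patients who will have glove changed prior to abdominal closure during CS", and "Arm 2 includes patients who will not have glove changed prior to abdominal closure during CS". On allocation it says "All patients are randomized using computer-generated sequences with allocation ratio 1:1", without saying when this happens relative to surgery. On timing of outcomes it says "Visit 1 is at 2-3 days post-surgery and visit 2 is at 30 ± 2 days post-surgery where primary and secondary outcomes are measured".

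Section 4 (Outcomes) blinds the clinicians who assess outcomes at the visits. It says nothing about whoever records a puncture in theatre.

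Section 5 names intention-to-treat as the population and adds "These 2 subgroups will be analyzed using intention-to-treat populations". It defines no modified population. Neither Section 5 nor Section 6 (Analyses) gives a method for missing outcomes.

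The sample size paragraph in Section 2 allows 5% for losses, taking 310 per group to 327. It has no separate allowance for women whose data collection is stopped.

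**The concern.** An intention-to-treat analysis needs an outcome, or a stated way of handling its absence, for every randomized woman. The stopping rule creates missing outcomes deliberately, on the basis of what happens to the gloves, and gloves are what the trial intervenes on.

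If removal were unrelated to arm, or unrelated to wound risk, the cost would be lost precision and a result limited to single-gloved, intact-glove operations. If it were related to both, the comparison would lose the protection of randomization. There is a plausible route. In Arm 1 the gloves come off before closure, which gives an extra moment at which a hole can be noticed. In Arm 2 they stay on. The plan describes no inspection common to both arms and no blinded recording of punctures. If punctured cases carry a higher wound risk and more of them are removed from Arm 1, that arm looks better even when changing gloves does nothing.

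Outcomes that were never collected cannot be recovered at analysis, so the conflict has to be settled before enrollment.

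**Working it through.** **Step 1: the text, without assumptions.**
- The stopping sentence stands apart from the exclusion criteria, so it reads as a rule for women already in the study.
- One item in it is surgery after the cesarean, which must come after the intervention. This makes the list most likely a post-randomization list, although the plan does not state when randomization takes place.
- Outcomes exist only at days 2-3 and 30 ± 2. A woman stopped in theatre has none.
- Section 5 includes every randomized woman, without exception.

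These statements cannot all be followed.

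**Step 2: the plan's own sample size.** With P1 = 0.064, P2 = 0.136, P = 0.10, and z-values 1.96 and 1.04, the plan's formula gives

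n = [1.96·√(2·0.10·0.90) + 1.04·√(0.064·0.936 + 0.136·0.864)]² / 0.072² = 310.9,

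in line with the stated 310. Then 310/0.95 gives 327 per group and 654 in total. The allowance is 327 − 310 = 17 women per arm for all losses. The planned difference is 13.6 − 6.4 = 7.2 points.

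**Step 3: possible bias with no true effect.** The documents give no puncture, detection or puncture-specific risk figures, so all inputs here are assumptions: puncture proportion π = 5%, 10% or 20%; complication risk 25% with puncture and 12% without, in both arms; proportion of punctures detected, and so removed, d = 0.8 in Arm 1 and 0.3 in Arm 2. The risk among women left in an arm is

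[π(1 − d)·0.25 + (1 − π)·0.12] / (1 − πd).

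At π = 10%, Arm 1 is (0.005 + 0.108)/0.92 = 12.28% and Arm 2 is (0.0175 + 0.108)/0.97 = 12.94%.

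| π | Arm 1 | Arm 2 | False benefit (points) | Share of 7.2 | Removed per 327, Arm 1 / Arm 2 |
|---|---|---|---|---|---|
| 5% | 12.14% | 12.46% | 0.33 | 5% | 13 / 5 |
| 10% | 12.28% | 12.94% | 0.66 | 9% | 26 / 10 |
| 20% | 12.62% | 13.94% | 1.32 | 18% | 52 / 20 |

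With 327 per arm less these removals, the two-sided type I error is 5.2%, 5.7% and about 7.5% instead of 5.0%.

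**Step 4: sensitivity to the decisive assumptions.** If d is the same in both arms, the formula gives the same value twice and the difference is zero. If risk is the same with and without puncture, it returns that risk in both arms and the difference is again zero.

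A second set of assumptions fixes overall risk at 13.6%, with 310 analyzed per arm, puncture in 5-20% and a risk ratio for puncture of 1.5 to 3. Detection of 80% vs 30% then gives 0.2 to 2.0 points (type I error up to 11.9%). Detection of 90% vs 10% gives 0.3 to 3.1 points (up to 22.4%).

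**Step 5: losses and power.** At π = 10%, Arm 1 loses 327 × 0.10 × 0.8 = 26 women, more than the 17 allowed. At 5% it loses 13, fewer than 17. The break-even is 17/(327 × 0.8) = 6.5% puncture, before any woman misses a visit. If glove events removed 2%, 5%, 10%, 15% or 20% of women in both arms on top of the 5% loss, power would be 84.3%, 83.2%, 81.2%, 78.9% or 76.4%, against the planned 85%.

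**The case against.** The strongest reply is that a conflict of wording is shown but a bias is not. A reader might infer that punctures *are* found more often in the glove-change arm and that the comparison *is* biased. The documents do not support that. They give no inspection procedure, puncture rate or detection rate. Control gloves also come off at the end of the operation, so holes may be found equally often. The 80% vs 30% split drives the result in Step 3, and even then the effect on type I error is small. All of this stands: *may bias* is as far as the text goes.

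Other points that stand:
- **Double gloving.** It is tempting to treat it as learned during surgery and chosen in light of the allocation. The plan gives no time for it, and it may be settled before incision. Whether the team knows the arm by then depends on the unstated timing of randomization.
- **Timing.** If allocation came just before closure, punctures already known would be pre-randomization exclusions. The plan does not say so, and Figure 1, the flow diagram that might show it, is not visible in the text at hand. The presence of surgery after the cesarean in the same list points the other way but does not settle the matter for glove events.
- **Loss allowance.** It is not necessarily used up; at 5% puncture it is not exceeded in Step 5.
- **Scope.** Limiting the question to intact single gloves can be a legitimate choice of estimand. Nothing in the documents shows that a change matters most when gloves are breached.

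None of this removes the conflict between Sections 2 and 5. A restricted population would have to be named, and this plan names intention-to-treat alone.

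**Conclusion.** The point holds as an inconsistency that carries a risk of bias. As written, the plan cannot both stop data collection on glove events and analyze all randomized women by intention-to-treat. This rests on the text alone, with one inference: that the removals follow randomization, which is likely but not stated.

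Bias needs two further conditions, unequal removal by arm and a link between puncture and wound risk. Neither is established, so its size is unknown. The illustration gives about 0.3 to 1.3 points in favor of glove change, roughly 5-18% of the planned 7.2, and the more extreme assumptions reach 3.1; zero remains possible. The loss of power is modest at low removal rates and takes power below 80% at about 15% removal. The reason to act is that the conflict is plain, missing outcomes cannot be restored later, and the remedy is cheap.

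**What to change.** 1. In Section 2, remove glove puncture and double gloving as reasons to stop data collection.
2. State that every randomized woman is followed to day 30 and analyzed in her allocated arm, and state when randomization takes place.
3. Record puncture and double gloving on the case report form for all women, and use them only in a sensitivity analysis.
4. Reconcile the other in-theatre data-collection stops in the same sentence (resuscitation and pelvic organ damage) with Section 5 in the same way. This concerns data collection only, not clinical care.

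The cost is a wording change and two form fields. No visits are added, because agreement to the one-month return is already an inclusion criterion. Keeping these women may slightly dilute the contrast between arms.

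If the sponsor wants only single-gloved, intact-glove operations, a uniform glove check in all women before allocation is revealed, just before closure, would turn glove events known by then into pre-randomization exclusions. That is a procedural redesign, would still miss punctures during closure, and is not part of the cheap fix.

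### The readable text does not say when women are randomised or when operators learn the arm; randomising when the team is ready to close would protect gloving and stop decisions made before then

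*Combined protocol and SAP*

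**What the plan says.** Section 2 (Study design) describes allocation in one sentence: "All patients are randomized using computer-generated sequences with allocation ratio 1:1". The readable text gives no time of randomisation, no concealment procedure and no point at which the operators are told the arm. The section refers to a flow diagram (Figure 1), which could not be seen for this review.

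The arms separate at a single moment: "Arm 1 includes patients who will have glove changed prior to abdominal closure during CS", and "Arm 2 includes patients who will not have glove changed prior to abdominal closure during CS".

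The same section lists events that end data collection. Two are clinical events in theatre: "Data collection will be stopped when pregnant women require cardiopulmonary resuscitation (CPR) or have damaged pelvic organs during CS". Two more concern gloving, and apply "when the surgical team has double gloving or the gloves get punctured during surgery". A further operation following the cesarean is the last ground. The section also has an exclusion that can arise shortly before the operation: "Exclusion criteria include pregnant women who have fever during labor".

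Section 4 (Outcomes) assigns assessment to "qualified medical practitioners who are blind to the intervention group assignment" and mentions no other blinding. Section 5 names intention-to-treat as the analysis population.

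**The concern.** Up to abdominal closure the two arms are meant to receive the same care, so the operators have no trial reason to know the arm before then. They cannot be blinded to the glove change itself, but they can be kept unaware of it until it is due. The readable text does not require this.

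The gap matters more here than in most trials because gloving is both the intervention and a ground for stopping data collection. Double gloving is the team's own choice. A puncture counts only if someone notices and reports it. A team that knows in advance whether fresh gloves are coming could double glove, replace gloves ad hoc or report punctures differently by arm. Double gloving and punctures then remove the woman from data collection, which conflicts with the stated intention-to-treat population. Blinded assessment at days 2–3 and day 30 cannot recover data that were never collected, or undo care that differed by arm.

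**Working it through.** **1. The plan's own figures.** Inputs from section 2: P1 = 0.064, P2 = 0.136, P = 0.10, Z = 1.96 and 1.04.

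n = (1.96·√(2·0.10·0.90) + 1.04·√(0.064·0.936 + 0.136·0.864))² / (0.136 − 0.064)² = 310.94 per group. The plan states 310; rounding up gives 311, a trivial difference. Then 310/0.95 = 326.3, rounded up to 327, and 2 × 327 = 654. The margin over 2 × 310 = 620 is 34 women. None of these figures is in dispute.

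**2. What randomising at readiness to close would and would not cover.**

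| Event | Covered? |
|---|---|
| Fever in labor (relevant only if allocation would otherwise precede or overlap labor) | Yes |
| Double gloving or ad hoc glove replacement before closure | Yes |
| Puncture noticed before closure | Yes |
| CPR or pelvic organ damage before closure | Yes |
| Puncture, or another stop event, during closure | No |
| Further surgery after the cesarean | No |
| How closure and later wound care are done | No |

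Keeping an earlier randomisation concealed until closure would also prevent early knowledge of the arm. Only randomising at that moment turns earlier stop events into women who were never randomised.

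**3. Losses under early allocation.** The documents give no rates, so 2%, 5% and 10% are assumptions for the share of women meeting an exclusion or stop rule between allocation and closure.

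- 654 × 0.02 = 13 lost, 641 left
- 654 × 0.05 = 33 lost, 621 left
- 654 × 0.10 = 65 lost, 589 left, which is below 620

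With the planned 5% loss to follow-up on top, each group has 327 × 0.95 × (1 − s) women, where s is the share stopped. That is 304.4, 295.1 or 279.6, with power 0.843, 0.832 or 0.812, against 0.851 with no stops. These figures describe precision only.

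**4. Bias if stopping differs by arm.** This is an illustration and every input except 327 is assumed: no true effect, 327 per arm, overall event risk 10% in both arms, and risk r among stopped women. The risk among women retained is (0.10 − s·r)/(1 − s). With r = 0.30 this is (0.10 − 0.03)/0.90 = 0.0778 for s = 10%, and (0.10 − 0.006)/0.98 = 0.0959 for s = 2%. The arm with more stops looks better although nothing differs. The chance of a significant result by a two-sided test at 0.05 (normal approximation) is:

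| Stopped, one arm vs the other | r = 30% | r = 20% |
|---|---|---|
| 5% vs 5% | 5.0% | 5.0% |
| 10% vs 5% | 8.1% | 5.7% |
| 10% vs 2% | 12.4% | 6.7% |
| 10% vs 0% | 16.1% | 7.5% |

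The table treats all stops alike. Late randomisation takes out only those made before closure.

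**The case against.** The strongest reply is that silence is not evidence of early allocation. Figure 1 may place randomisation, and a reader with the full protocol should look. A reader might infer that women are allocated at admission, or that surgeons here know the arm throughout the operation. The documents support neither inference; they only fail to rule them out. This stands, and it is why the point is put as something the readable text does not state.

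A reader might also infer that late release solves the problem of unblinded operators. It does not, as the uncovered rows in the working show. The larger share of the remedy may lie with the stop rule: following stopped women and analysing them as randomised protects the comparison from their loss, whenever the allocation is opened. That also stands, and it is part of the fix. It does not replace late randomisation, because follow-up cannot undo gloving choices already made with the arm known.

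Finally, the loss counts do not measure bias. Losses of 13 or 33 fit within the 34-woman margin, although 33 leaves almost nothing for missed visits. With equal stopping in the two arms the illustration shows no inflation at all. Both criticisms are correct.

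**Conclusion.** The point holds in a limited form. The readable text leaves open when women are randomised and when operators learn the arm, in a trial where the arms separate at one late moment, only assessors are blinded, and two team-dependent gloving events end data collection under a stated intention-to-treat analysis.

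The size is unknown because the plan gives no stop rates. Losses of about 13, 33 or 65 of 654 women follow from assumed rates of 2%, 5% or 10%. In the illustration, the false-positive rate stays at 5.0% with equal stopping and runs from 5.7% to 16.1% across the unequal cases. Those values rest wholly on the assumed stop rates and event risks and are not estimates for this trial. A larger sample would not correct such a bias.

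The documents do not show that differential conduct would occur, or that late randomisation would protect anything after closure begins.

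**What to change.** State in section 2 that:

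- Consent, eligibility and baseline data are completed before surgery.
- Randomisation takes place by opening a concealed, sequentially numbered allocation only when the team is ready to begin abdominal closure, after confirming that no exclusion or stop event has occurred. That moment is recorded as the date and time of randomisation.
- Women who fail this check are logged as not randomised, with the reason.
- Women with a stop event after randomisation are still followed for outcomes and analysed as randomised. Section 5 should say the same.

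If Figure 1 already fixes the time of randomisation, the text should match it and add when the operating team is told.

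The cost is small: protocol wording, preparation of the concealed allocations, a brief step at closure, and fresh gloves to hand in every case. The documents do not describe theatre staffing, so the hospital would have to name who opens the allocation. The planned 654 randomised women is unchanged, but some consented women will never be randomised. At the assumed rates of 2%, 5% or 10%, consent would be needed from 654/0.98 = 668, 654/0.95 = 689 or 654/0.90 = 727 women (rounded up).
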